5.1.2. Rituximab

5.1.2.1. Formulation/Packaging/Storage

Rituximab is a highly purified, 1328-amino acid antibody with an approximate molecular mass of 145 kD. The chimeric mouse/human anti-CD20 antibody is a glycosylated IgG₁ κ immunoglobulin containing murine light and heavy chain variable regions and human γ₁ heavy chain and κ light chain constant regions.

Rituximab is a sterile, clear, colorless, preservative-free liquid concentrate for intravenous (IV) administration. Rituximab is supplied at a concentration of 10 mg/mL in either 100 mg (10 mL) or 500 mg (50 mL) single-use vials. The product is formulated for intravenous administration in 9.0 mg/mL sodium chloride, 7.35 mg/mL sodium citrate dihydrate, 0.7 mg/mL polysorbate 80, and Sterile Water for Injection. The pH is adjusted to 6.5.

Rituximab vials are stable at 2° to 8°C (36° to 46°F). Rituximab vials should be protected from direct sunlight. Rituximab solutions for infusion are stable at 2° to 8°C (36° to 46°F) for 24 hours and at room temperature for an additional 24 hours. However, since rituximab solutions do not contain a preservative, diluted solutions should be stored refrigerated (2° to 8°C). No incompatibilities between rituximab and polyvinylchloride or polyethylene bags have been observed.

5.1.2.2. Dose and Administration

The recommended dosage of rituximab is 375 mg/m² given as an IV infusion.

Preparation for Administration: Use appropriate aseptic technique. Withdraw the necessary amount of rituximab and dilute to a final concentration of 1 to 4 mg/mL into an infusion bag containing either 0.9% Sodium Chloride USP or 5% Dextrose in Water USP. Gently invert the bag to mix the solution. Discard any unused portion left in the vial. Parenteral drug products should be inspected visually for particulate matter and discoloration prior to administration.

Administration: DO NOT ADMINISTER AS AN INTRAVENOUS PUSH OR BOLUS. Infusion and hypersensitivity reactions may occur. Premedication, consisting of acetaminophen and diphenhydramine, should be considered before each infusion of rituximab. Premedication may attenuate infusion-related events. Since transient hypotension may occur during rituximab infusion, consideration should be given to withholding anti-hypertensive medications 12 hours prior to rituximab infusion.

First Infusion: The rituximab solution for infusion should be administered intravenously at an initial rate of 50 mg/hr. Rituximab should not be mixed or diluted with other drugs. If hypersensitivity or infusion-related events do not occur, escalate the infusion rate in 50 mg/hr increments every 30 minutes, to a maximum of 400 mg/hr.

Rituximab infusion should be interrupted for severe reactions. In most cases, the infusion can be resumed at a 50% reduction in rate (e.g., from 100mg/hr to 50mg/hr) when symptoms have

completely resolved. Most patients who have experienced non-life-threatening infusion-related reactions have been able to complete the full course of rituximab therapy

5.1.2.3. Subsequent infusions: If the subject tolerated the first infusion well, subsequent Rituximab doses may be mixed in a total volume of 250 mL NS and administered at an initial rate of 100mL/hr for 30 minutes, then 200mL/hr for 60 minutes such that the entire dose is delivered over 90 minutes. If the first infusion was not well tolerated, the guidelines for the first infusion should be followed for the subsequent infusions. Overdose

There has been no experience with over-dosage of rituximab in human clinical trials. Single doses higher than 500 mg/m² have not been tested in controlled studies.

5.1.2.4. Dose Modification for Adverse Reactions

The dose of rituximab generally remains constant throughout the trial. Rituximab infusion should be interrupted for severe reactions, e.g., rapid tumor lysis. Treatment of infusion-related symptoms with diphenhydramine and acetaminophen is recommended. Additional treatment with bronchodilators or IV saline may be indicated. Epinephrine, antihistamines, and corticosteroids should be available for immediate use in the event of a hypersensitivity reaction to rituximab (e.g., anaphylaxis). In most cases, the infusion can be resumed at a 50% reduction in rate (e.g., from 100mg/hr to 50mg/hr) when symptoms and laboratory abnormalities have completely resolved.

Infusions should be discontinued in the event of serious or life-threatening cardiac arrhythmias. Subjects who develop clinically significant arrhythmias should undergo cardiac monitoring during and after subsequent infusions.

Subjects who meet the following criteria should be discontinued from the study:

- Active HBV infection or hepatitis
- Severe or life-threatening anaphylaxis or hypersensitivity reaction

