3. STUDY DESIGN

3.1. Overview of Study Design

The rationale for the study concept is provided in [Section 1.3](#).

This is a phase II trial evaluating the safety and efficacy of the combination of Ibrutinib and Rituximab as primary treatment of cGVHD. We plan to enroll 35 patients on this study. Patients will be formally monitored monthly for 12 months to evaluate for outcome and safety endpoints. All other assessments will be done at the physician's discretion or institutional standards. All patients, responders and treatment failures, will be followed for a period of one year from the time of initiation of therapy. The primary endpoint will be the proportion of patients that are alive and off all systemic IST at 12 months following initiation of treatment.

Eligible patients will be those with a first episode of symptomatic cGVHD, requiring systemic immunosuppression for control of symptoms. Following study entry, patients will be started on:

[figure not shown]
1. Ibrutinib 420mg PO QDAY (28-day cycles) for a total of 12 cycles unless discontinued early due to toxicity (see stopping rules in section 5.1.1.4). Dose adjustments are required for patients with hepatic impairment or those receiving concomitant voriconazole or posaconazole or other strong CyP 3A4 inhibitor according to sections 5.1.1.5 and 5.1.1.6.
2. Rituximab 375mg/m² IV weekly x 4 weeks (to be started on study day 7 ± 3 days), then 375mg/m² IV q3months x 4 doses (months 4, 7, 10, 13).

Additional cGVHD treatment will include:

- **Sirolimus** (target level 4-10 ng/mL) – patients currently receiving a calcineurin inhibitor (tacrolimus or cyclosporine) and/or mycophenolate mofetil for GVHD prophylaxis will be converted to sirolimus per institutional guidelines. In the case of contraindication or intolerance to sirolimus, another systemic immunosuppressive (IS) drug (i.e. tacrolimus or cyclosporine) may be substituted at the discretion of the treating investigator.
- Short-course corticosteroids may be used, if necessary, for more rapid symptom control (≤1mg/kg Medrol, with planned taper to be completed no longer than 4 weeks).

When cGVHD manifestations have been quiescent for at least 4 weeks, sirolimus (or other IS medication) should be tapered over 4 weeks or per investigator discretion.

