5.1.1.4. Dose Modification for Non-Cardiac Adverse Reactions

The dose of study drug must be modified according to the dose modification guidance in [Table 1](#) and [Table 2](#) if any of the following non-cardiac toxicities occur:

- Grade 4 neutropenia (ANC <500/ μ L) for more than 7 days. See [Section 6.1](#) for instructions regarding the use of growth factor support.
- Grade 3 thrombocytopenia (platelets <50,000/ μ L) in the presence of clinically significant bleeding events.
- Grade 4 thrombocytopenia (platelets <25,000/ μ L).
- Grade 3 or 4 nausea, vomiting, or diarrhea if persistent, despite optimal anti-emetic and/or anti-diarrheal therapy.
- Any other Grade 4 or unmanageable Grade 3 non-cardiac toxicity

Adverse events that are considered related to concomitant high dose corticosteroids (e.g. hyperglycemia, insomnia) do not require dose modification or holding of ibrutinib.

If the dose of ibrutinib is reduced, at the investigator's discretion, the dose of ibrutinib may be re-escalated after 4 weeks of a dose reduction in the absence of a recurrence of the toxicity that led to the reduction. Dose changes must be recorded in the CRF.

Table 1. Ibrutinib Dose Modifications

Occurrence	Action to be Taken
First	Withhold study drug until recovery to Grade ≤ 1 or baseline; may restart at original dose level
Second	Withhold study drug until recovery to Grade ≤ 1 or baseline; may restart at 1 dose level lower (i.e., 280 mg/day for 420 mg/day dose)
Third	Withhold study drug until recovery to Grade ≤ 1 or baseline; may restart at 1 dose level lower (i.e., 140 mg/day for 420 mg/day dose; 280 mg/day)
Fourth	Discontinue study drug

Table 2. Ibrutinib Dose Reduction Levels

Starting Dose Level	140 mg	280 mg	420 mg
Dose Reduction Level 1	70 mg	140 mg	280 mg
Dose Reduction Level 2	Discontinue	70 mg	140 mg
Dose Reduction Level 3	NA	Discontinue	Discontinue

For required dose modification for hepatic impairment refer to [Section 5.1.1.5](#) and for concomitant treatment with CYP3A inhibitors refer to [Section 5.1.1.6](#).

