8.1. Screening Phase

8.1.1. Screening/Consenting Visit

Required testing for the screening visit:

- Medical History
- Physical examination with vital signs, height, weight
- Schirmer's Test
- Karnofsky Performance Status (Appendix B)
- Serum Pregnancy test
- Hepatitis Serologies (HepBsAg, HepBsAB, HepC)
- Fasting lipid panel
- Laboratory evaluation per institutional guidelines including CBC with differential, glucose, BUN, creatinine, total bilirubin, alkaline phosphatase, LDH, albumin, SGOT(AST), SGPT (ALT), CRP, CK, calcium, and magnesium.
- IgG level
- Biomarkers (correlative lab studies)

- Pulmonary Function Test
- GVHD assessment form (Appendix E)
- GVHD self-report form (Appendix F)

Eligibility criteria will be verified, and ineligible patients will proceed off study and no further follow-up will be obtained.

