9.2. Criteria for Study Discontinuation

Patients may be withdrawn from the study if:

- The patient requests withdrawal
- If the patient develops side effects that are considered life-threatening
- If the patient refuses to have treatment as recommended
- If the patient refuses to have tests that are needed to determine whether the treatment is safe and effective
- If the agents used in this study cease to be available
- If other causes prevent continuation of the study
- For any other reason that the physician feels it may be necessary that the patient discontinue the study

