10. STATISTICAL METHODS AND ANALYSES

10.1. Analysis Population

All treated subjects

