10.4. Efficacy Analysis Methods

This is a phase II trial evaluating the safety and efficacy of ibrutinib and rituximab as primary treatment of cGVHD. Efficacy and safety endpoints will be estimated according to the cumulative incidence and Kaplan-Meier methodology in the presence of competing risks. Outcomes will be compared to historical values based on the Gray's test and log rank test respectively. We plan to enroll 35 patients on this study. Patients will be formally monitored for 12 months to evaluate for outcome and safety endpoints (efficacy/safety visits at the completion of month 1, 2, 3, 6, 9, and 12). All other assessments will be done at the physician's discretion or institutional standards. All patients, responders and treatment failures, will be followed for a period of one year. The primary outcome measure will be the proportion of patients that are alive and off all systemic immunosuppression at 12 months following initiation of treatment. The primary endpoint will be estimated according to the Kaplan-Meier methodology in the presence of competing risks. Outcome will be compared to historical values based on the log rank test. Secondary outcome measures will be cGVHD response, cumulative steroid exposure, time to discontinuation of systemic immunosuppression, requirement for second-line cGVHD therapy, non-relapse and overall mortality, failure-free survival and safety. Secondary survival endpoints will be estimated according to the Kaplan-Meier methodology in the presence of competing risks, and outcomes will be compared to historical values based on the log rank test. Secondary time-to-event endpoints will be estimated according to cumulative incidence methodology, and outcomes will be compared to historical values based on the Gray's test (Gray 1988).

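### Leaving the study for rituximab toxicity is not reconciled with one-year follow-up of all patients, and the plan does not say how such patients count in the primary endpoint

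*Combined protocol and SAP*

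**What the plan says.** The combined protocol and SAP handles exits for toxicity in three ways.

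- **Rituximab (5.1.2.4).** "Subjects who meet the following criteria should be discontinued from the study". The criteria are active HBV infection or hepatitis, and severe or life-threatening anaphylaxis or hypersensitivity. The exit is from the study, not only from the drug.
- **General withdrawal (9.2, repeated in 12.10).** "Patients may be withdrawn from the study if" one of several reasons applies. One is "If the patient develops side effects that are considered life-threatening"; another is refusal of treatment as recommended. This is permission, not a direction.
- **Ibrutinib (5.1.1.4, Table 1).** The last step is "Discontinue study drug". Table 3 in 5.1.1.5 likewise stops only the drug.

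On follow-up, section 3.1 says: "All patients, responders and treatment failures, will be followed for a period of one year from the time of initiation of therapy". Section 10.4 repeats the one-year promise. The analysis population in 10.1 is "All treated subjects".

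On analysis, 10.3 sizes the study as a one-sample binomial test of a proportion in 35 patients. Section 10.4 says: "The primary endpoint will be estimated according to the Kaplan-Meier methodology in the presence of competing risks". It gives no rule for censoring or for a missing month-12 status. Section 6.3 does assign an outcome to one exit: new systemic therapy for worsening cGVHD is a treatment failure. No section does so for exits due to toxicity.

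**The concern.** The primary endpoint is a proportion among all treated patients at a fixed time. It needs a month-12 status, or a rule in its place, for each of them. A patient who leaves because of a severe reaction, possibly at an early infusion, has neither assured.

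Two other sections suggest that leaving the study ends protocol assessment. For patients off study because of new systemic therapy, 9.1 stops adverse event reporting and leaves further follow-up to institutional practice. Section 10.3 allows replacement of some withdrawn patients to protect power, which presumes that a withdrawn patient may give no usable outcome. That replacement covers only losses and withdrawals unrelated to treatment, so toxicity exits are neither replaced nor classified.

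A Kaplan-Meier analysis without a stated rule would normally censor such a patient on leaving. That treats the patient as having the same later chance of success as those who stayed. If the true chance is lower, the estimate is too high, and a regimen that causes more toxicity exits can look more effective.

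**Working it through.** **Inputs.** From 10.3: null rate 0.55, alternative 0.75, one-sided alpha 0.05, N = 35, power 80%. Assumed, because the documents give no figure: the number k of treated patients who leave for toxicity without a month-12 status (1 to 4), and their chance of success w.

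**The plan's own figure.** With the one-sided normal approximation,

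n = [(1.645 × √(0.55 × 0.45) + 0.842 × √(0.75 × 0.25)) / 0.20]² = 34.97, rounded up to 35.

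The stated sample size reproduces. The exact binomial test at n = 35 rejects at 25 or more successes, with error 3.5% and power 75.8%.

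**Effect of leaving k patients out.** This approximates censoring them early. If p is the true rate in all 35, the rate among those who remain is

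(35p − kw) / (35 − k).

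For example, with p = 0.75, k = 1 and w = 0 it is 26.25/34 = 77.2%. With k = 4 and w = 0.25 it is (26.25 − 1)/31 = 81.5%.

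The error columns give the chance that an exact one-sided test on the remaining patients rejects 0.55 when the true rate in all 35 is 55%. The size column is that test's error when no bias is present.

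| k | n left | Rejects at | Exact size, no bias | True 75% reads as, w = 0 | True 75% reads as, w = 0.25 | Error, w = 0 | Error, w = 0.25 |
|---|---|---|---|---|---|---|---|
| 0 | 35 | 25 | 3.5% | 75.0% | 75.0% | 3.5% | 3.5% |
| 1 | 34 | 24 | 4.7% | 77.2% | 76.5% | 6.9% | 5.8% |
| 2 | 33 | 24 | 2.9% | 79.5% | 78.0% | 6.4% | 4.5% |
| 3 | 32 | 23 | 3.9% | 82.0% | 79.7% | 11.9% | 7.4% |
| 4 | 31 | 23 | 2.3% | 84.7% | 81.5% | 11.3% | 5.8% |

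If the withdrawn patients have the same chance as the rest, w = p, the formula returns p and there is no bias.

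**Reading the error columns.** Part of the change from 3.5% comes from the test being discrete. At k = 1 the unbiased size is already 4.7%, so the bias accounts for the step from 4.7% to 6.9% (w = 0) or 5.8% (w = 0.25).

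**One patient at the threshold.** With 24 successes, 24/35 gives p = 0.073 and 24/34 gives p = 0.047. Whether one withdrawn non-success stays in the denominator decides the test.

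**The case against.** A reader might infer that all patients harmed by treatment leave the study, have no month-12 outcome and are censored. The documents do not support that.

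- Only the two criteria in 5.1.2.4 carry a direction to leave. Withdrawal for life-threatening side effects is optional, and refusal of treatment need not be caused by treatment.
- No section ends follow-up for these patients. Where the protocol means to end it, it can say so: under 8.1.1, "ineligible patients will proceed off study and no further follow-up will be obtained". Section 9.1 otherwise sets completion at the later of 12 months and 30 days after the last ibrutinib dose. Section 5.1.2.4 deals with dose modification and may simply be loose wording for stopping treatment.
- No censoring rule is written. The binomial design on 35 patients, with replacement limited to reasons unrelated to treatment, suggests that toxicity exits keep their place in the denominator. The historical 56% equals 14/25, all patients enrolled in that trial. It does not fit the 22 evaluable patients (12/22 = 54.5%, 13/22 = 59.1%).
- A withdrawn patient known to have died, or to have received new systemic therapy for worsening cGVHD, is a non-success anyway.
- The error rates put an exact binomial test on a reduced denominator, which is neither the test in 10.3 nor the method in 10.4. The exclusions for positive HBV PCR and known severe hypersensitivity (4.2) should also keep exits few.

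All of this limits the claim. It does not remove the gap: the sections still conflict, what 10.3 suggests is not a rule, and 10.4 names a method whose default handling of early exits is censoring. If the historical 56% used all enrolled patients, dropping exits here would also make the comparison uneven.

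**Conclusion.** The concern holds in a limited form. The directed exits in 5.1.2.4 and the permitted ones in 9.2 and 12.10 are not reconciled with 3.1, 10.1 and 10.4, and the plan does not say how these patients count in the primary endpoint. They are not assured a month-12 status. Censoring is the default under the named method, not something the plan states.

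The size is illustrative. It rests on an assumed 1 to 4 exits in 35 and on omission standing in for early censoring. Measured against the assumed effect of 20 points, the upward bias at a true 75% is 2.2 to 9.7 points if every withdrawn patient is a non-success, 1.5 to 6.5 points at a 25% chance of success, and zero if their chance equals the rest. The one-sided error at a true 55% is 6.4% to 11.9% in the worst case and 4.5% to 7.4% at 25%. A general statement that the error rate is lost would therefore go too far, since one of these cases stays below 5%. The point should be corrected because the primary result can turn on a single patient and the correction is a matter of wording.

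**What to change.** 1. In 10.2.1 and 10.4, state that every treated patient is in the primary denominator with the observed month-12 status. State that a treated patient withdrawn for toxicity or non-adherence whose status is unknown counts as a non-success and is not censored.
2. Add one sensitivity analysis that uses observed outcomes only.
3. Reconcile 5.1.2.4, 9.2 and 12.10 with 3.1 and 10.4 by separating stopping treatment from leaving the study. A patient who stops treatment stays in follow-up for vital status and IST use to month 12 unless consent is withdrawn.

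The first change settles the analysis; the third keeps the number of unknown outcomes small. The clinical criteria for stopping treatment are not touched. The cost is a wording amendment and the collection of two items, survival and IST use, at a single centre. The reported success rate may be slightly lower, because some patients of unknown status would count as non-successes.

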6. CONCOMITANT MEDICATIONS/PROCEDURES

6.1. Permitted Concomitant Medications

Supportive medications in accordance with standard practice (such as for emesis, diarrhea, etc.) are permitted.

Usage of antimicrobial prophylaxis in accordance with standard practice is permitted and should be considered in subjects who are at increased risk for opportunistic infections.

Use of neutrophil growth factors (filgrastim and pegfilgrastim) or red blood cell growth factors (erythropoietin) and transfusion is permitted in accordance with institutional policy.

Short courses (< 28 days) of steroid treatment are permitted at doses that do not exceed 1.0 mg/kg per day of methylprednisolone or equivalent.

Ancillary therapy and supportive care for cGVHD is permitted as outlined in the NIH Consensus Development Project 2014 Ancillary Therapy and Supportive Care Working Group Report (Carpenter 2015). In particular, the use of topical therapies (e.g. inhaled steroids, azithromycin, and monteleukast for bronchiolitis obliterans, budesonide for anorexia/nausea, steroid and/or tacrolimus rinses for oral symptoms, cyclosporine eye drops for xerophthalmia) will not be considered systemic therapy for cGVHD.

6.2. Medications to be Used with Caution

6.2.1. CYP3A Inhibitors/Inducers

Ibrutinib is metabolized primarily by CYP3A4. Concomitant use of ibrutinib with drugs that strongly or moderately inhibit CYP3A4 can increase ibrutinib exposure. Dose adjustment of ibrutinib due to concomitant use of CYP3A4 inhibitors should follow Table 4 (Section 5.1.1.6)

Avoid concomitant use of systemic strong CYP3A4 inducers (e.g., carbamazepine, rifampin, phenytoin, and St. John's Wort). Consider alternative agents with less CYP3A4 induction.

A list of common CYP3A4 inhibitors and inducers is provided in [Appendix C](#). For further information, please refer to the current version of the [IB](#) and examples of inhibitors, inducers, and substrates can be found at <http://medicine.iupui.edu/clinpharm/ddis/main-table/>. This website is continually revised and should be checked frequently for updates.

6.2.2. Drugs That May Have Their Plasma Concentrations Altered by Ibrutinib

In vitro studies indicated that ibrutinib is not a substrate of P-glycoprotein (P-gp), but is a mild inhibitor. Ibrutinib is not expected to have systemic drug-drug interactions with P-gp substrates. However, it cannot be excluded that ibrutinib could inhibit intestinal P-gp and BCRP after a therapeutic dose. There is no clinical data available. Therefore, to avoid a potential interaction in the GI tract, narrow therapeutic range P-gp substrates such as digoxin or methotrexate, should be taken at least 6 hours before or after ibrutinib.

